7.2 Duration of Participation

Describe how long subjects will be involved in this research study. Include the number of sessions and the duration of each session - consider the total number of minutes, hours, days, months, years, etc.

Subjects will be enrolled in this study for a total of six months, starting at enrollment in PHP, and continuing to their final 6-month follow-up visit. They will have study interventions at 0, 3, and 6 weeks, and again at six months. They will take study medication while in PHP, and stop once six weeks of study duration is completed. Duration of PHP is individualized, but is on average about 8 weeks. Duration of PHP will not be dependent upon study participation.

7.3 Test Article(s) (Study Drug(s) and/or Study Device(s))

7.3.1 Description

Provide a brief description of all test articles (drugs (including any foods and dietary supplements), devices and/or biologics used in the research including the purpose of their use and their approval status with the Food and Drug Administration (FDA). Include information about the form of the drug product (e.g., tablets, capsules, liquid).

The Penn State Health IDS pharmacy will purchase Naltrexone 50mg tablets from a pharmaceutical wholesaler. The IDS pharmacy will purchase gelatin capsules and USP grade methylcellulose from a pharmacy supplier to be used for compounding the active and placebo capsules. For the active Naltrexone 50mg capsules, a Naltrexone 50mg tablet will be placed in an empty gelatin capsule with methylcellulose filler. The placebo capsules will be empty gelatin capsules filled with Methylcellulose.

The Food and Drug Administration has approved oral naltrexone for the treatment of alcohol use disorder and for blockade of opioid receptors⁷. This medication is not approved for the specific use of treatment of eating disorder, impulsive behavior, or self-injurious behavior.

7.3.2 Treatment Regimen

Describe dose, route of administration and treatment duration. Include information about dose adjustments.

All subjects receiving study medication will receive oral naltrexone 50mg oral tablets, blinded as described above. All subjects receiving placebo will receive methylcellulose, blinded as described above. All capsules, regardless of contents, will be administered by mouth once daily, at a time of day to be chosen by the study participant.

In pediatric autism literature, doses between 0.5-2 mg/kg are described^{8,11,22,22-25}, though in adult eating disorder literature doses of 50-100mg are described^{13,14,16-18}. Food and Drug Administration labelling of oral naltrexone for treatment of alcohol use disorder and opioid receptor blockade describe an appropriate maintenance dose of 50mg per day⁷. Therefore subjects will receive 50mg of oral naltrexone a day if they are randomized to the medication group. Patients with body weight less than 25kg are excluded from the study so that no participant will exceed the maximum described pediatric dose of 2 mg/kg. Participants receiving

study article will receive 25mg of naltrexone for three days, followed by increase to study dose of 50mg/day The maximum daily dose is 50mg.

Participants will take study medication daily while they are in PHP or for six weeks total. That is, if a participant is in PHP for three weeks, they will take the study medication for the entirety of their time in PHP and then continue to take the medication for three additional weeks after discharge from PHP. If a participant is in PHP for twelve weeks—which is quite uncommon—they will only take study medication for six weeks.

For participants who complete PHP early, they will be asked to complete the same battery of surveys at 3 and 6 weeks, at weeks 8/9 for post-treatment evaluation, and at 6 months. Survey responses will be obtained via RedCAP for participants not on-site at time of survey completion.

Participants who, upon completion of the study, feel that they had significant benefit from the study article which lost upon withdrawal of the study article, are eligible for open label oral naltrexone therapy if desired. Participants will be asked at subsequent medical and behavioral health follow-up appointments if they felt they benefitted from the study article. If they feel they did, they will be offered a prescription for oral naltrexone to start at 25mg/day for three days and then 50mg a day after.

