The subject will be provided with oral naltrexone or placebo weekly from the MSHMC research pharmacy. Subjects will be given one weeks' worth of medication at a time. Subjects will be randomized at enrollment to receive either study drug (naltrexone) or placebo. Participants or parents of minor participants will be provided study drug or placebo following completion of urine drug screen and consent/assent. Patients will take the medication daily while they are in programming; after completion of programming or withdrawal from the study they will no longer be given study medication. For subjects who are enrolled in child PHP and who eat meals with parents, the families may choose to administer study drug during meals at programming. For adult patients enrolled in adult programming, subjects may choose to self-administer the medication.

On their first contact with PHP, all patients in Adult PHP complete various eating disorder indices as a part of routine care, including the ED-15, PHQ-9, GAD-7, and EDE-Q. This battery of indices is repeated every 3 weeks while a patient is in programming.

For those who are enrolled in this study, they will complete their routine indices, in addition they will also complete the BIS/BAS and the ABUSI at enrollment and at weeks 1, 3, and 6 while enrolled in the study. Participants will also be asked to take the routine indices (ED-15, EDE-Q, PHQ, GAD, BIS/BAS, and ABUSI) at week 8 or 9 for a post-treatment evaluation. These will be taken in an in-person medical appointment or electronically via RedCap

6 months after enrollment, subjects will be sent copies of ED-15, EDE-Q, PHQ, GAD, BIS/BAS, and ABUSI indices either in an in-person medical appointment or via RedCap to complete. If the patient returns for medical follow-up between 5 and 7 months after enrollment, their height, weight, and body mass index will also be recorded to determine if weight restoration was maintained.

Patients in Child PHP typically complete a different inventory every three weeks as part of routine care. If a patient choses to participate in this study they will be asked to complete the same surveys as participants in Adult PHP (ED-15, GAD-7, and PHQ-9), and they will receive the same amount and type of compensation as those who already take them as part of standard of care.

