7.3.5 Blinding of the Test Article

Describe how the test article is blinded.

The Penn State Health IDS pharmacy will purchase Naltrexone 50mg tablets from a pharmaceutical wholesaler. The IDS pharmacy will purchase gelatin capsules and USP grade methylcellulose from a pharmacy supplier to be used for compounding the active and placebo capsules. For the active Naltrexone 50mg capsules, a Naltrexone 50mg tablet will be placed in an empty gelatin capsule with methylcellulose filler. The placebo capsules will be empty gelatin capsules filled with Methylcellulose.

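### The 25 mg three-day lead-in in section 7.3.2 cannot be delivered from the capsules that the protocol describes, which hold either a whole 50 mg tablet or placebo

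*Combined protocol and SAP*

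**What the plan says.** **Dose (7.3.2).** Participants receiving "study article will receive 25mg of naltrexone for three days, followed by increase to study dose of 50mg/day". The same section sets the active dose in general terms: "All subjects receiving study medication will receive oral naltrexone 50mg oral tablets, blinded as described above", and later "Therefore subjects will receive 50mg of oral naltrexone a day if they are randomized to the medication group". It sets the frequency too: "All capsules, regardless of contents, will be administered by mouth once daily". The daily maximum is 50 mg. The 25 kg weight floor is justified as keeping every participant at or below 2 mg/kg.

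**The lead-in looks deliberate.** For participants who want open-label drug after the study, 7.3.2 repeats the schedule: "they will be offered a prescription for oral naltrexone to start at 25mg/day for three days and then 50mg a day after".

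**Product.** Section 7.3.1 describes the active capsule: "For the active Naltrexone 50mg capsules, a Naltrexone 50mg tablet will be placed in an empty gelatin capsule with methylcellulose filler". Section 7.3.5, which defines the blind, describes the comparator: "The placebo capsules will be empty gelatin capsules filled with Methylcellulose". The same paragraph appears in 7.3.6.1, and its two capsule sentences again in 7.3.6.3. Only 50 mg tablets are purchased.

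**Supply and handling.** Section 7.3.6.1 supplies seven capsules at a time. Section 7.3.4 says that study and clinic staff neither handle nor administer the medication. Section 8.1 plans 30 participants per arm.

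**The concern.** The section that sets the dose asks for something that the sections describing the product do not provide. None of them mentions a 25 mg capsule, a half tablet, a first-week pack or an instruction for days 1-3. The gap cannot be closed at the clinic, because staff do not handle the capsules. It has to be closed at compounding, and that is where the text is silent.

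The stake is the first three doses in the active arm. A pharmacist working from the product text would supply 50 mg from day 1. One working from 7.3.2 would have to devise a product and a labelling scheme that the blinding section does not cover. The lead-in is also worded only for the naltrexone arm, so nothing says that placebo participants get the same day 1-3 instructions. Section 10.0 lists nausea and abdominal pain among the risks of naltrexone, so a gentler start plausibly serves tolerability, although 7.3.2 gives no reason for it.

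**Working it through.** No sample size, power or alpha figure is involved. The check compares the doses reachable from the described products with the schedule required.

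**Inputs**
- Required: 25 mg/day on days 1-3, then 50 mg/day (7.3.2).
- Products described: capsules of 50 mg or 0 mg (7.3.1, 7.3.5, 7.3.6.1, 7.3.6.3).
- Frequency: once daily (7.3.2). Supply: seven capsules at a time (7.3.6.1).
- Course: six weeks = 42 days (7.3.2).
- Active arm: 30 planned (8.1). Weight floor: 25 kg (3.2 and 7.3.2).

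**1. Is the lead-in reachable?** Each day gives 0 or 50 mg, so three-day totals can only be 0, 50, 100 or 150 mg. The lead-in needs 3 × 25 = 75 mg. That is not in the set, so skipping a day does not reach it either.

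**2. Size if the product text is followed**

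| Period | As described | As required by 7.3.2 | Comparison |
|---|---|---|---|
| Days 1-3 | 3 × 50 = 150 mg | 3 × 25 = 75 mg | 150/75 = 2 |
| Week 1 | 7 × 50 = 350 mg | 75 + 4 × 50 = 275 mg | 350/275 = 1.27 |
| 42 days | 42 × 50 = 2100 mg | 75 + 39 × 50 = 2025 mg | 75/2025 = 3.7% more |

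The doses affected are 3 of 42 (7.1%).

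**3. Against the protocol's limits.** At the 25 kg floor, day 1 would be 50/25 = 2 mg/kg instead of 25/25 = 1 mg/kg. This equals, and does not exceed, the 2 mg/kg that 7.3.2 accepts, and 50 mg is the stated daily maximum.

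**4. Does the remedy fit the supply?** Three 25 mg capsules plus four 50 mg capsules make seven, so the weekly count and once-daily dosing are unchanged. The lead-in needs 3 × 30 = 90 capsules of 25 mg, or 90/2 = 45 tablets if halved. Both arms together need 2 × 30 = 60 week-1 packs.

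**The case against.** The best defence is that this is an omission and not a contradiction. The lead-in sentence is specific and sequenced, and it is best read as qualifying the general 50 mg sentences around it. Seven capsules a week and once-daily dosing both fit a 3 + 4 pack. The product paragraph explains how the 50 mg capsules are made and does not say that no other strength will exist. Being repeated, it is one omission and not several independent ones. The pharmacy that compounds every capsule could make a 25 mg one, and a pharmacy order or manual outside these documents may already provide for it.

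Most of this stands. It rules out reading 7.3.2 as contradicting itself, and the capsule count and frequency are not evidence of conflict. It does not remove the gap. The sections that should describe every product and how it is blinded describe two capsules, and neither can give the required first doses.

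Three stronger readings are tempting, and the documents do not support them.
- **A safety breach.** A 50 mg start is within both stated limits, and the documents give no figure for harm from it.
- **A broken blind.** Opening a capsule could show a tablet or only powder, but nothing says that participants would be told to open one. Placebo has no dose to step up; it needs only the same labels and instructions.
- **A larger share of the course.** Section 7.2 Study Procedures says that "after completion of programming or withdrawal from the study they will no longer be given study medication", which could suggest a shorter course. That is a separate inconsistency about duration. Section 7.3.2 expressly continues dosing to six weeks after early discharge, so 42 days is the basis used here.

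**Conclusion.** The point holds: the lead-in required by 7.3.2 cannot be given from the products described. If the product text is followed, up to 30 participants receive twice the stated dose for three days, 27% more in week 1 and about 3.7% more over six weeks. These figures assume full adherence, a 42-day course and no 25 mg capsule arranged elsewhere. If a pharmacy document already provides one, the doses will be right and only the protocol text needs completing.

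The consequence is limited to early dosing fidelity and possibly early tolerability. A reader might infer that the efficacy comparison is compromised. The documents do not support that: the comparisons in 8.3 are at three weeks, six weeks and six months, all well after day 3, and neither the sample size nor the analysis depends on the lead-in. It should be fixed because it concerns the first doses given and the remedy is simple.

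**What to change.** **If the lead-in is intended, as it appears to be:**
- Add a 25 mg active capsule (half a 50 mg tablet plus methylcellulose in the same shell) to 7.3.1, 7.3.5, 7.3.6.1 and 7.3.6.3. This assumes that the pharmacy can halve the tablets accurately.
- Dispense week 1 in both arms as an identical-looking pack labelled days 1-3 and days 4-7, seven capsules in all, with the same instructions for every participant.
- Qualify the general 50 mg sentences in 7.3.2 with 'from day 4'.

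**If the sponsor confirms that the lead-in is not intended:** delete that sentence from 7.3.2. The choice of schedule is a clinical one for the sponsor.

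**Cost.** One extra compounding and labelling step in week 1 by the pharmacy that already makes the capsules: 90 capsules of 25 mg from 45 tablets, and 60 labelled packs at full enrolment. Visits, sample size and analysis do not change. If a pharmacy manual already covers the lead-in, the cost is a few lines of protocol text.

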7.1 Study Design

Describe and explain the study design.

This is a double-blind, randomized, placebo-controlled study. We have developed the following schedule of events. All events with a superscript $^{\circ}$ are for study purposes only and are not part of the standard of care:

	Pre-Enrollment Screening: Medical	Enrollment	Week 1	Week 2	Week 3	Week 4	Week 5	Week 6 (end of treatment	Week 8-9 (post- treatment)	Six Months
Intervention								_	>	
Initial Medical Assessment	Х									
Subsequent Medical Assessment, including comprehensive review of systems			x		x		x		х	х
Initial Psychiatry Assessment	X									
Subsequent Psychiatric Assessment, including suicidal ideation			х	х	х	х	х	х	х	х
Discussion of risks and benefits, inclusion and exclusion criteria ^o		х								
Consent/Assent ^o		Х								
\$25 Greenphire Clincardo		Х								х
Urine Drug Screen ^o		Х								
Serum Pregnancy Test (female participants)°		х								
Urine Pregnancy Test (female participants)°					х			х		
Administer Study Article ^o			Х	Х	х	Х	Х	х		
EKG	X									
AST	X				Xº			Xº		
ALT	Х				χ°			Xo		
Total Bilirubin	Х				Xº			Xº		
Direct bilirubin	Х				Xº			Xº		
Heart Rate	Х		Х	Х	Х	Х	Х	Х	Х	Х
BMI	X		Х	Х	Х	Х	Х	X	Х	Х
Height	X		Х	X	X	X	Х	X	X	Х
Weight	X		X	X	X	X	X	X	X	X
Blood Pressure	X		X	X	X	X	X	X	X	X
Temperature Adverse event monitoring ^o	Х		X	x	x	x	x	x	X	X
Suicidal Ideation Screening (ASQ			^	^	^	^	^			
for age <17or C-SSRS for age 18+)		х	Х	Х	х	Х	Х	х	Х	Х
ED-15		Х	х		х			Х	X	х
EDE-Q		Х	х		х			Х	X	Х
ABUSI°		Х	Х		х			Х	Х	Х
GAD-7		Х	х		х			Х	Х	Х
PHQ-9		Х	Х		Х			Х	X	Х
BIS/BAS°		Х	Х		Х			Х	Х	Х

Note: Medical assessments may occur in weeks 1,3 etc or 2,4 etc depending on standard of care for that patient. As long as patients are seen within a 14 day interval (2 week timeframe), the exact week intervals (1,3 or 2,4) may vary. Additionally, the 6 month follow up appointment may take place any time between 5-7 months after study enrollment ends.

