9.2 Data that are reviewed

Describe the data that are reviewed, including safety data, untoward events, and efficacy data.

Participants in this study will take the study article daily while they are enrolled in program. When they complete program, they will no longer be obliged to take the study article, nor will they be required to have weekly psychiatric evaluation, laboratory evaluation, or suicide assessments. Patients in PHP have at least one medical follow-up appointment two weeks after they complete program, and further follow-up based on the patient's needs.

During the course of the trial, we will monitor:

- New diagnoses of depression, anxiety, suicidal thoughts, suicidal ideation, self-injurious behavior and related diagnoses via chart review. Monitoring for these new diagnoses is a part of routine care of PHP
- The results of every-three-weeks liver function tests
- The results of every-three-weeks urine pregnancy tests in female participants
- Vital signs
- The results of the behavioral health surveys
- New diagnoses of abdominal pain, nausea, vomiting, headache, or fatigue regardless of relationship to diagnosis of eating disorder, though these are common problems in eating disorder treatment
- New diagnoses of jaundice, liver failure, elevated transaminases, rash, or other medical problems that are uncommon in the treatment of eating disorder.
- New diagnosis of pregnancy
- Length of participation in PHP, as patients who are experiencing good results with the study article may require a shortened length of stay in program
- Need for escalation of eating disorder or mental health care, such as need for inpatient
 hospitalization for medical stabilization of eating disorder or other medical diagnosis, need for
 residential care for eating disorder,
- Incidence of death or serious bodily harm
- Incidence of acute withdrawal from narcotic agents (expected to be zero due to preparticipation urine drug screen, though this is a serious event)

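### For participants who finish the partial hospitalization program before week 6, the protocol both stops and continues study drug, and Section 9.2 lifts weekly suicide screening that the schedule keeps

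*Combined protocol and SAP*

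**What the plan says.** **Study drug after early completion of PHP**

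- Section 7.3.2 (Treatment Regimen) works the case through. A participant with a three-week stay takes drug in PHP and will "then continue to take the medication for three additional weeks after discharge from PHP", making six weeks in all.
- The schedule in Section 7.1 marks the "Administer Study Article" row in each of weeks 1 to 6 and labels week 6 as the end of treatment.
- Section 7.2 (Study Procedures) says that "after completion of programming or withdrawal from the study they will no longer be given study medication".
- Section 9.2 says: "When they complete program, they will no longer be obliged to take the study article".
- Section 7.2 (Duration of Participation) has drug taken during PHP and stopped at six weeks. It does not say what happens when PHP ends first.

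**Weekly suicide screening after early completion**

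- The schedule marks the ASQ/C-SSRS row at enrollment, in every week from 1 to 6, at week 8-9 and at six months, with no exception for people who have left PHP. The row lacks the superscript given to events that "are for study purposes only and are not part of the standard of care", so the schedule treats screening as routine care.
- Section 9.1 has the results reviewed weekly for all participants.
- Section 9.2 says of those who have completed program: "nor will they be required to have weekly psychiatric evaluation, laboratory evaluation, or suicide assessments". It adds that PHP patients have "at least one medical follow-up appointment two weeks after they complete program".
- Section 9.3 ties weekly screening to being in care and weekly chart review to being in program.

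**The concern.** Someone who finishes PHP at week 3, 4 or 5 falls under two incompatible dosing instructions, both in current text. Pharmacy and clinic staff could stop or continue supply for identical participants and each be following the protocol.

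Two things are at stake.

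- **Exposure.** Section 8.3 compares outcomes at three and six weeks. If the Study Procedures rule is followed, an early completer reaches the week-6 ED-15 having been off drug since discharge. Section 9.2 itself expects that patients doing well on study article may need a shorter stay, so early completion could be related to response. That is a reason to settle the rule in advance. It does not give a size for any bias.
- **Safety.** Section 10.0 lists depression, mood changes and occasional worsening of self-injurious behavior as risks, and participants may be as young as 13. Anyone still taking blinded drug after discharge should have an unambiguous requirement for weekly screening. Section 9.2 removes that requirement, and Section 9.3's reference to being in care is not defined for a person who has been discharged but is still dosed.

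**Working it through.** The plan states no figure on this point to reproduce, so the check is a comparison of texts plus simple counts.

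**Step 1. Set the rules side by side for a participant leaving PHP before week 6.**

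| Source | Study drug | Weekly suicide screen |
|---|---|---|
| 7.1 schedule | Weeks 1-6 | Weeks 1-6 |
| 7.2 Study Procedures | Not given after PHP | Not addressed |
| 7.2 Duration of Participation | Not settled | Not addressed |
| 7.3.2 | Six weeks in total | Not addressed (surveys only) |
| 9.1 | Not addressed | Reviewed weekly for all |
| 9.2 | No obligation after PHP | Not required after PHP |
| 9.3 | Not addressed | Weekly while in care |

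The dosing column cannot be reconciled: one section ends supply and another continues it. In the screening column, 9.2 conflicts with 7.1 and 9.1.

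**Step 2. Size of the dosing difference.** Inputs: once-daily dosing, 25 mg for three days and then 50 mg (7.3.2); seven capsules per weekly supply (7.3.6.1). Let w be the week of discharge.

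- Days if stopped = 7w; days if continued = 42.
- Active-arm mg = 3 × 25 + (days − 3) × 50.
- Six weeks: 75 + 39 × 50 = 2,025 mg.

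| w | Days, stop vs continue | Active mg if stopped | Active mg if continued | Weekly supplies |
|---|---|---|---|---|
| 3 | 21 vs 42 | 75 + 18 × 50 = 975 | 2,025 | 3 vs 6 |
| 4 | 28 vs 42 | 75 + 25 × 50 = 1,325 | 2,025 | 4 vs 6 |
| 5 | 35 vs 42 | 75 + 32 × 50 = 1,675 | 2,025 | 5 vs 6 |

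**Step 3. Screens affected, only if 7.3.2 dosing is combined with 9.2 monitoring.**

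- Scheduled screens whose requirement lapses = 6 − w = 3, 2, 1 for w = 3, 4, 5.
- Days on drug after discharge = 42 − 7w = 21, 14, 7.

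**Step 4. Credit the remaining contacts in the same scenario.** Surveys remain at week 6 (7.3.2), and a medical visit falls at week w + 2, that is week 5, 6 or 7 (9.2). Weeks on drug with no required screen, survey or medical visit:

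- w = 3: week 4 only, so 1.
- w = 4: week 5 only, so 1.
- w = 5: none, so 0.

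Even in those weeks, adverse-event monitoring is a study row in the schedule. Sections 7.3.4 and 7.3.6.1 also bring a dosed participant to the clinic for each new week's supply and the return of unused capsules. That visit is a contact, though not a suicide screen.

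**The case against.** The strongest reply is that the protocol contains a coherent plan and only needs its stray sentences corrected. Section 7.3.2 is the regimen section, addresses this exact case and agrees with the schedule. Dosing under 7.3.2 with monitoring under 7.1 runs to week 6 on both counts, and Section 9.1 supports it. Section 9.2 is also coherent on its own terms, because it releases drug and weekly assessments together. A gap in screening on drug appears only when the dosing rule of one section is joined to the monitoring rule of the other. This stands, and it limits the safety point to a conditional one. It does not remove the dosing contradiction, and it does not tell staff which coherent reading governs.

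A reader might also infer that Section 9.2 cancels the week-6 liver and urine pregnancy tests. The documents do not support that. The waived items are described as weekly, while Section 9.2's own list keeps the three-weekly liver and pregnancy tests. The schedule marks these on-treatment tests as study-only, Section 7.1.2 requires a liver panel every three weeks for study participants, and Section 15.1 names the six-week liver test as study-specific.

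Finally, an average PHP stay of about 8 weeks exceeds the six-week drug period, and no one staying six weeks or longer is affected. That is correct, but no spread is given. Sections 7.3.2 and 19.1.1 both make provision for people who leave PHP before week 6, so the case is foreseen.

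**Conclusion.** The contradiction on study drug is real and should be corrected. For the protocol's own week-3 example it is the difference between 21 and 42 days of dosing before the six-week comparison. The statement on suicide assessments in Section 9.2 also conflicts with Sections 7.1 and 9.1. Applied to someone still dosed under Section 7.3.2, it removes the requirement for 3, 2 or 1 scheduled screens after discharge at week 3, 4 or 5.

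A reader might conclude that the plan necessarily leaves adolescents on blinded drug unmonitored. It does not. That result depends on one pairing of sections, Section 9.2 removes a requirement without forbidding screening, and weekly dispensing, the week-6 surveys, adverse-event questioning and a medical visit remain. Nor do the documents support any figure for lost power or bias, since the number of early completers is not stated and the pilot sample size rests on no power calculation.

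The counts assume discharge at the end of week 3, 4 or 5, full adherence, and a medical visit exactly two weeks after program.

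**What to change.** This is a correction of wording that uses a rule the protocol already contains.

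- Take Section 7.3.2 as governing: six weeks of study article regardless of PHP discharge.
- Correct the sentences in Section 7.2 (Study Procedures) and Section 9.2 that stop drug or release participants from it. Section 7.2 (Duration of Participation) needs at most a clarifying word.
- State in Sections 9.2 and 9.3 that weekly ASQ/C-SSRS screening and weekly safety review continue until the last dose whether or not the participant is still in PHP. Screening can be done at the weekly dispensing contact or remotely.

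The liver and urine pregnancy tests need no new provision.

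The cost is an amendment, matching consent wording, and a brief weekly screen for those who leave PHP early. Weekly contact is already implied by seven-capsule dispensing, and no extra participants are needed.
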